6.3.2.1 Which baseline ultrasound metric best predicts positive response to NAC?

Response to NAC will be dichotomized into a yes/no response according to the RECIST guidelines, and the predictive ability of each baseline ultrasound metric will be analyzed by constructing separate ROC curves.

6.3.2.2 Which baseline ultrasound metric correlates most strongly with absolute reduction in tumor size (diameter, area, volume)?

The relationship between ultrasound metric values at baseline and absolute change in tumor size from baseline to end of chemotherapy type will be visualized by scatterplots. If the relationship appears linear and monotonic, the correlation will be assessed by Pearson regression.

6.3.2.3 What is the combined ability of any 2 baseline ultrasound metrics for prediction of positive response to NAC?

With response to NAC dichotomized into a yes/no response, the combined predictive ability will be analyzed by constructing separate ROC curves for combinations of any 2 ultrasound metrics.

6.3.2.4 Do serial changes in ultrasound metrics correlate with reduction in tumor size following NAC?

The relationships between serial changes in ultrasound metrics and tumor size will be visualized by scatterplots. If monotonic and linear, the correlation between serial change in ultrasound metrics and change in tumor size (area) will be analyzed by Pearson regression. Assessments of serial change will be made at 3 intervals per chemotherapy type: baseline, early chemotherapy type treatment, and end of chemotherapy type treatment.

6.3.2.5 Serial change in which of the 8 ultrasound metrics best predicts positive response to NAC?

Response to NAC will be dichotomized into a yes/no response, and the predictive ability of serial change in each ultrasound metric from 0-6 weeks will be analyzed by constructing separate ROC curves.

6.3.2.6 Do combinations of changes over time in any ultrasound outcome metrics correlate with reduction in tumor size following NAC?

Assuming linear relationships exists between serial change in ultrasound metrics and serial change in tumor size following NAC, multiple linear regression models will be constructed for each of the 8 ultrasound metrics. The model outcome will be change in tumor size, and model predictors will be serial change in any 2 ultrasound metrics.

6.3.2.7 Which combinations of serial change for any 2 ultrasound metrics best predicts positive response to NAC?

Positive response to NAC will be dichotomized into a yes/no response, and the predictive ability of serial change in ultrasound metrics from baseline to end of

chemotherapy type will be analyzed by constructing separate ROC curves for combinations of any 2 ultrasound metrics.

6.3.2.8 What is the combined performance of ultrasound metrics and mammography for predicting a reduction in tumor size following NAC?

Reduction in tumor size will be dichotomized into a yes/no response. We will select ultrasound metrics with an AUC exceeding 0.75 in 6.3.2.1, 6.3.2.3, 6.3.2.5, and 6.3.2.7, and their combined diagnostic accuracy with mammography measures (mass size, density, shape, and margins) will be analyzed in separate ROC curves.

6.3.2.9 What are the sensitivity, specificity and PPV of ultrasound outcome metrics for identifying masses that positively respond to treatment?

Best-balanced cutpoints from the highest performing ultrasound metrics in 6.3.2.1 and 6.3.2.3 will be derived from ROC curves, using Youden's Index. These cutpoints will be used to analyze the PPV of positive response to NAC (dichotomized as a yes/no variable).

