2.1.3 Determine the combined diagnostic accuracy of ultrasound metrics and mammography.

For ultrasound outcome metrics (singly or combined) with AUC exceeding 0.75 in 2.1.1 and 2.1.2, we will determine if combining the metrics with mammography-derived mass size, density, shape, and margins improves ROC performance relative to not combining with mammography.

2.1.4 Determine which cutpoints for ultrasound metrics detect malignancy with optimum sensitivity and specificity.

Best-balanced cutpoints from the highest performing ultrasound metrics in 2.1.1 will be derived, and PPV will be calculated.

2.2 Aim #2: Quantify the ability of ultrasound-derived stiffness, elasticity, viscosity, and anisotropy to predict a positive response to treatment.

In 40 women with newly diagnosed invasive breast cancer who are scheduled to begin clinically indicated NAC, ARFI, VisR, and DDAI imaging will be performed (as described in Aim #1) immediately before beginning treatment and then over the course of treatment. The eight ARFI, VisR, and DDAI outcome metrics described in Aim #1 will be statistically correlated with clinically determined change in tumor size following NAC treatment. ARFI, VisR, and DDAI outcome metrics will also be evaluated for ability to predict positive response to NAC, with positive response determined according to the RECIST guidelines.^{1,2}

2.2.1 Determine which baseline ultrasound metric best predicts positive response to NAC.

We will statistically determine, from among all eight ultrasound outcome metrics acquired at each imaging time point, which metric best predicts positive response to treatment, with positive response determined according to the RECIST guidelines.^{1,2}

2.2.2 Determine which baseline ultrasound metric correlates most strongly with absolute reduction in tumor size.

We will correlate absolute change in tumor size (diameter and area) from baseline to end of chemotherapy type with ultrasound metric values at baseline.

2.2.3 Determine the combined ability of any 2 baseline ultrasound metrics for prediction of positive response to NAC.

We will systematically combine all possible groupings of any two ultrasound outcome metric values at baseline. We will then statistically analyze the combined ability to predict reduction in tumor size.

2.2.4 Determine if serial changes in ultrasound metrics correlate with positive response to NAC.

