6.0 STATISTICAL CONSIDERATIONS

6.1 Study Design/Study Endpoints

For Aims #1 and #2, the ability of ultrasound biomarkers to discriminate binary outcomes (malignant/benign and responsive/unresponsive to treatment) will be analyzed using logistic regression. The area under the receiver operating characteristic curve (AUC) will be quantified, with separate models fit for each of the eight ultrasound biomarkers. Because most ultrasound biomarkers are continuous measures, the best-balanced cutpoints optimizing sensitivity and specificity will be calculated, using Youden's Index. Outcome discrimination by dual biomarkers will be analyzed in 28 separate models with combinations of any two ultrasound biomarkers. The combined benefit of ultrasound and mammography will be analyzed in 32 models, by adding a single mammography metric (lesion size, density, shape, or margins) to each of the eight ultrasound biomarker models. In Aim #2, the relationship between biomarker values and tumor size, biomarker values and change in tumor size, and change in biomarker values and change in tumor size will be analyzed by linear regression. These correlations will be analyzed in separate models for each of the eight ultrasound biomarkers, in models of dual ultrasound biomarkers, and in models combining mammography metrics with ultrasound biomarkers.

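### The tumour-size correlations in 6.3.2.2 and 6.3.2.4 are computed only for metrics that pass a visual linearity check, with no method for the rest, and 6.1 promises linear regression for all eight

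*Combined protocol and SAP*

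**What the plan says.** Section 6.3.2.2 poses a ranking question: "Which baseline ultrasound metric correlates most strongly with absolute reduction in tumor size (diameter, area, volume"). Its method starts with a plot: baseline metric values against "absolute change in tumor size from baseline to end of chemotherapy type will be visualized by scatterplots". It then continues: "If the relationship appears linear and monotonic, the correlation will be assessed by Pearson regression". Nothing follows for a metric whose plot does not qualify, and no criterion or assessor is named for the visual judgement.

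Section 6.3.2.4 repeats the condition for serial change: "If monotonic and linear, the correlation between serial change in ultrasound metrics and change in tumor size (area) will be analyzed by Pearson regression". Section 6.3.2.6 builds its two-metric models on an assumption of linearity and gives no alternative.

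Two other places carry no such condition. Objective 2.2.2 reads: "We will correlate absolute change in tumor size (diameter and area) from baseline to end of chemotherapy type", to be related to baseline metric values. Section 6.1 covers metric values against size change as well as change against change. It ends that list with "change in biomarker values and change in tumor size will be analyzed by linear regression" and adds: "These correlations will be analyzed in separate models for each of the eight ultrasound biomarkers".

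No rank correlation, transformation or nonlinear model appears anywhere in the documents.

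**The concern.** A ranking needs the same measure for every candidate. Under 6.3.2.2 a metric receives a coefficient only if someone, looking at the outcome data, judges its plot straight enough. A metric that is strongly but nonlinearly related to shrinkage then has no value to rank, and the metric named strongest is only the strongest among those that passed.

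Curvature is plausible here. Two of the eight metrics are ratios (of PD and of RE) and others, such as τ, are positive quantities, for which skewness is common. Section 6.3.2.2 also names three size measures, so eight metrics give 8 × 3 = 24 visual decisions. Diameter, area and volume are nonlinear functions of one another, so a metric could pass for one and fail for another.

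Section 6.1 would keep every metric in, but by a straight-line fit. An analyst cannot tell from the text which section governs, and neither provides a measure suited to a monotone but curved relation.

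**Working it through.** **No plan figure to reproduce.** The only power statement (section 6.2) concerns the AUC. The check is a comparison of the sections, followed by an illustration under assumed inputs.

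**Step 1: what each section does with a curved metric.**
- 6.3.2.2 and 6.3.2.4: Pearson if the plot qualifies; otherwise nothing is stated.
- 6.1: a linear model for each of the eight metrics. With one predictor, Pearson r = slope × SD(metric) / SD(size change), so this amounts to Pearson without the gate.

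**Step 2: detection of a single metric.** The sample size of 40 is from section 6.2. The rest is assumed:
- size change y = 0.5·z + √(1 − 0.5²)·e = 0.5·z + √0.75·e, with z and e standard normal;
- metric = z (linear) or exp(s·z) (log-normal, log-SD s);
- detection = two-sided p < 0.05;
- a quadratic term with p < 0.05 stands in for a plot that does not look linear, so the gated plan detects only if Pearson p < 0.05 and quadratic p ≥ 0.05.

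| Metric | Gated plan | Ungated Pearson | Spearman |
|---|---|---|---|
| Linear | 88% | 93% | 89% |
| Log-SD 0.25 | 84% | 92% | 89% |
| Log-SD 0.5 | 74% | 90% | 89% |
| Log-SD 0.75 | 63% | 86% | 89% |
| Log-SD 1.0 | 55% | 80% | 88% |

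These are simulation estimates; repeat runs put the last gated figure between 54% and 56%. At log-SD 1.0 about 32% of metrics fail the stand-in screen.

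**Step 3: where the loss comes from.** At log-SD 1.0 the gap between the gated plan and Spearman is 88 − 55 = 33 points. Dropping the gate alone recovers 80 − 55 = 25 of them; moving from Pearson to Spearman adds 88 − 80 = 8. At log-SD 0.5 dropping the gate recovers 90 − 74 = 16 points, and Spearman is then 1 point below ungated Pearson. At 0.25 Spearman is 3 points below it.

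**Step 4: the ranking itself.** Section 6.3.2.2 asks for a ranking and sets no test, so a second illustration is closer to its question. Metric A is linear with true correlation 0.4. Metric B is exp(k × latent normal) with latent correlation 0.6, so B is the stronger (k = 0 denotes B untransformed). The sample size is again 40, with 10,000 replicates.

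| k | Mean Pearson r for B | B above A by Pearson | B above A by Spearman |
|---|---|---|---|
| 0 | 0.59 | 89% | 87% |
| 1 | 0.50 | 74% | 87% |
| 1.5 | 0.44 | 59% | 86% |
| 2 | 0.39 | 49% | 87% |

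Mean Spearman for B is about 0.57 throughout. If the gate removes B, it ranks above A in 0% of replicates by construction.

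**The case against.** The best reply is that 6.3.2.2 does not say a metric failing the check is left out. Plotting before using Pearson is ordinary practice, the omission is only a missing alternative branch, and 6.1 gives every metric a linear model. A reader might infer that the plan definitely excludes curved metrics; read as a whole, the documents do not establish that. What they establish is a conflict between 6.1 and 6.3.2.2, with no suitable method under either.

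A reader might also take the 33-point gap as the expected loss. The documents do not support that. They give no distribution for any metric, log-SD 1.0 is strong skew, the gap is only 5 points (89 − 84) at log-SD 0.25, and the quadratic test is not a visual judgement.

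Nor is Spearman free. It roughly matches the gated plan on linear data (89% against 88%) but trails ungated Pearson (93%), and it does not rescue non-monotone relations.

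Finally, consequences are limited. The ROC analyses of response in 6.3.2.1, 6.3.2.3, 6.3.2.5 and 6.3.2.7 do not use the gate, and in section 6.3 the mammography and cutpoint steps draw on those. Objective 2.2.9 does point to 2.2.4, the serial-change correlation, but its counterpart 6.3.2.9 points to ROC analyses instead.

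All of this narrows the point. It does not supply the missing method or settle which section governs.

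**Conclusion.** The point stands as a specification defect with a practical consequence. Followed as written, 6.3.2.2 and 6.3.2.4 leave a metric that fails the visual check without a coefficient; followed under 6.1, such a metric stays in but can be understated. Either route can change which metric is named strongest.

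Under the assumptions shown, detection is about 84% down to 55% with the gate, 92% down to 80% with ungated Pearson, and 88–89% with Spearman across log-SD 0.25 to 1.0. Most of the loss is due to the gate rather than to Pearson. These figures depend on the assumed skew, the latent correlation of 0.5 and the stand-in for the visual check; they are not estimates for this trial.

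Severity is minor to moderate. The study describes itself as exploratory, and no later step in section 6.3 uses the 6.3.2.2 ranking. The documents do not support extending the point to the malignancy or RECIST-response conclusions.

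**What to change.** - In 6.3.2.2 and 6.3.2.4, drop the visual condition. For all eight metrics and each named size measure, compute Spearman's correlation with a bootstrap 95% confidence interval, and rank on it in 6.3.2.2.
- Where a woman contributes several rows, as serial imaging allows, resample by woman.
- Keep the scatterplots, Pearson coefficients and linear fits as description. The plots would still show a non-monotone relation, which Spearman does not capture.
- Align 6.1 with this, so that one section does not promise unconditional linear regression while another makes it conditional.
- In 6.3.2.6, say what happens if the assumed linearity is not met; a single-metric rank correlation does not settle that.

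The cost is a few sentences and no new data. The statistical price is about 9% asymptotic efficiency against ungated Pearson if the data are exactly bivariate normal: (3/π)² = 0.91. In the illustration that is about 89% against 93% detection on linear data.

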7.0 STUDY MANAGEMENT

7.1 Institutional Review Board (IRB) Approval and Consent

It is expected that the IRB will have the proper representation and function in accordance with federally mandated regulations. The IRB should approve the consent form and protocol.

In obtaining and documenting informed consent, the investigator should comply with the applicable regulatory requirement(s), and should adhere to Good Clinical Practice (GCP) and to ethical principles that have their origin in the Declaration of Helsinki.

Before recruitment and enrollment onto this study, the patient will be given a full explanation of the study and will be given the opportunity to review the consent form. Each consent form must include all the relevant elements currently required by the FDA Regulations and local or state regulations. Once this essential information has been provided to the patient and the investigator is assured that the patient understands the implications of participating in the study, the patient will be asked to give consent to participate in the study by signing an IRB-approved consent form.

Prior to a patient's participation in the trial, the written informed consent form should be signed and personally dated by the patient and by the person who conducted the informed consent discussion.

7.2 Required Documentation

Before the study can be initiated at any site, the following documentation must be placed on file (as applicable).

- A copy of the official IRB approval letter for the protocol and informed consent
- IRB membership list
- CVs and medical licensure for the principal investigator and any sub-investigators who will be involved in the study.
- Investigator's signature documenting understanding of the protocol and providing commitment that this trial will be conducted according to all stipulations of the protocol College of American Pathologist (CAP) and Clinical Laboratory Improvement Amendments (CLIA) Laboratory certification numbers and institution lab normal values.

7.3 Registration Procedures

Patients will be registered into OnCore®, a web based clinical research platform by one of the Study Coordinators. The spreadsheet contains each subject enrolled in the study identified by the patient first and last initial, study id, date of enrollment into study, race and ethnicity.

7.4 Data Management and Monitoring/Auditing

All data management will be performed by the senior graduate student research assistant working on this project, with supervision and guidance from the study PI, [name]. Automated methods are already in place to manage data acquisitions and storage. First, all raw data files acquired by the Siemens ultrasound system are labeled by the date and time of acquisition. Next, data files are stored into file folders labeled according to the assigned patient participant number 1-100 (which in no way reflects identifiable patient information). The data are processed using custom software developed in Matlab and/or C++, and the processed data files are stored in subfolders under each patient participant number. Analysis of the processed data often includes image rendering as well as assessment of contrast; contrast-to-noise; mean, median and standard deviation of relevant parameter values, etc. ROC analysis will also be performed. The results of data analysis will be stored with appropriate labeling indicating the corresponding patient number. Note that data storage will occur using secure UNC servers that meet the current standards for PHI security.

7.5 Adherence to the Protocol

Except for an emergency situation in which proper care for the protection, safety, and well-being of the study patient requires alternative treatment, the study shall be conducted exactly as described in the approved protocol.

7.5.1 Emergency Modifications

UNC and Affiliate investigators may implement a deviation from, or a change of, the protocol to eliminate an immediate hazard(s) to trial subjects without prior UNC or their respective institution's IRB/IEC approval/favorable opinion.

For any such emergency modification implemented, a UNC IRB modification form must be completed by UNC Research Personnel within five (5) business days of making the change.

7.5.2 Single Patient/Subject Exceptions

Any request to enroll a single subject who does not meet all the eligibility criteria of this study requires the approval of the UNC Principal Investigator and the UNC IRB.

7.5.3 Other Protocol Deviations/Violations

According to UNC's IRB, a protocol deviation is any unplanned variance from an IRB approved protocol that:

- Is generally noted or recognized after it occurs
- Has no substantive effect on the risks to research participants
- Has no substantive effect on the scientific integrity of the research plan or the value of the data collected
- Did not result from willful or knowing misconduct on the part of the investigator(s).

An unplanned protocol variance is considered a violation if the variance meets any of the following criteria:

- Has harmed or increased the risk of harm to one or more research participants.
- Has damaged the scientific integrity of the data collected for the study.
- Results from willful or knowing misconduct on the part of the investigator(s).
- Demonstrates serious or continuing noncompliance with federal regulations, State laws, or University policies.

If a deviation or violation occurs please follow the guidelines below:

Protocol Deviations: UNC personnel will record the deviation in OnCore®, and report to any sponsor or data and safety monitoring committee in accordance with their policies. Deviations should be summarized and reported to the IRB at the time of continuing review.

Protocol Violations: Violations should be reported by UNC personnel within one (1) week of the investigator becoming aware of the event using the same IRB online mechanism used to report UPIRSO.

Unanticipated Problems Involving Risks to Subjects or Others (UPIRSO):

Any events that meet the criteria for "UPIRSO" as defined by UNC's IRB must be reported by the Study Coordinator using the IRB's web-based reporting system.

7.6 Amendments to the Protocol

Should amendments to the protocol be required, the amendments will be originated and documented by the Principal Investigator at UNC. It should also be noted that when an amendment to the protocol substantially alters the study design or the potential risk to the patient, a revised consent form might be required.

The written amendment, and if required the amended consent form, must be sent to UNC's IRB for approval prior to implementation.

7.7 Record Retention

Study documentation includes all eCRFs, data correction forms or queries, source documents, Sponsor-Investigator correspondence, monitoring logs/letters, and regulatory documents (e.g., protocol and amendments, IRB correspondence and approval, signed patient consent forms).

Source documents include all recordings of observations or notations of clinical activities and all reports and records necessary for the evaluation and reconstruction of the clinical research study.

Government agency regulations and directives require that all study documentation pertaining to the conduct of a clinical trial must be retained by the study investigator. In the case of a study with a drug seeking regulatory approval and marketing, these documents shall be retained for at least two years after the last approval of marketing application in an International Conference on Harmonization (ICH) region. In all other cases, study documents should be kept on file until three years after the completion and final study report of this investigational study.

7.8 Obligations of Investigators

The Principal Investigator is responsible for the conduct of the clinical trial at the site in accordance with ethical principles originating from Title 21 of the Code of Federal Regulations and/or the Declaration of Helsinki, which are consistent with International Conference on Harmonisation (ICH)/Good Clinical Practice (GCP) guidelines, and in accordance with applicable local and legal requirements. The Principal Investigator is responsible for personally overseeing the treatment of all study patients and ensuring that clinical data associated with biospecimen(s) collection should be used and disclosed only for research in compliance, as applicable, with HIPAA, with the U.S. Department of Health and Human Services and FDA human subjects protection regulations and with applicable State and local laws. The Principal Investigator must assure that all study site personnel, including sub-investigators and other study staff members, adhere to the study protocol in accordance with the guidance and regulations listed above both during and after study completion.

The Principal Investigator will be responsible for assuring that all the required data will be collected and entered into the eCRFs. Periodically, monitoring visits will be conducted and the Principal Investigator will provide access to his/her original records to permit verification of proper entry of data. At the completion of the study, all eCRFs will be reviewed by the Principal Investigator and will require his/her final signature to verify the accuracy of the data.

